### **XI. DATA ANALYSIS**

**a. Plan of Analysis.** Based on previous research and our preliminary data, we anticipate  $\geq 18\%$  of patients will be non-adherent to screening guidelines. As such, we will enroll 450 patients to identify  $\geq 90$  non-adherent patients. To test **Specific Aim 1 - Hypotheses 1A/1B**, we will use (a) a one sample test of improvement in adherence at follow-up and (b) a two-sample comparison of post-intervention adherence across intervention conditions. These analyses will allow us to establish preliminary effect sizes for powering the subsequent NIH submission. The first test will compare % adherent at follow-up against a null value of 15% improvement (i.e., % of non-adherent subjects who would become adherent over 150 days without intervention). We think this is an unrealistically high null value, but it was chosen to avoid overestimating the impact of the study interventions. Using this null value, a one-tailed test with  $\alpha=0.05$ , and  $\geq 90$  non-adherent subjects across conditions, we will have power of 0.80 to observe improvement as small as 10% over the null (40% relative improvement). The second test will use  $\chi^2$  to compare conditions. Given a one-tailed test with  $\alpha=0.10$  and 45 non-adherent subjects in each condition, we will have power of 0.70 to observe a difference as small as 24% in adherence at follow-up. More importantly, we will establish a 95% confidence interval around the overall improvement rate (across conditions) with  $\leq 10.4\%$  margin of error and intervention specific rates of improvement with  $\leq 14.8\%$  margin of error. These intervals will allow us to calculate power for the subsequent trial under expected, ideal, and worst-case scenarios. Patients lost to follow-up will be considered intervention failures (i.e. non-adherent) in accordance with intention-to-treat principles. In order to test **Specific Aim 2 - Hypothesis 2**, we will use hierarchical, multinomial logistic regression to predict adherence at baseline. Given our sample size and an expected adherence rate of 0.80, at  $\alpha=0.05$ , we will have power  $\geq 0.70$  to observe odds ratios as small as 1.33. Any covariates demonstrating a  $p$ -value  $\leq 0.10$  will be addressed when refining the interventions for the subsequent NIH trial. **Specific Aim 3** is focused on the qualitative feedback data collected at the 150-day follow-up call. Qualitative data analysis of the feedback data will include open and axial coding under Grounded Theory principles examined in the context of subject demographic characteristics. The codes/concepts that emerge from these data will be examined in the context of the demographic characteristics of the subjects providing feedback. Results will then be used to refine the intervention protocols for the subsequent efficacy trial.

**b. Additional Analyses.** Supplemental analyses will be performed in order to strengthen interpretations of potential intervention effects. Specifically, we will perform the analyses described above among only those women who were referred to UR WHP (i.e., those without a usual provider of women's healthcare). Although we are not specifically powering our study around this subset of subjects, these analyses may help us identify success within this underserved population or important covariates/barriers than must be addressed when intervening with subjects lacking a usual women's healthcare provider. We will also corroborate subject self-reports of contact and screening using UR WHP records and subject eRecords (for those with providers associated with UR Medicine) as a way to further validate the findings observed. Finally, we will evaluate over-referral in our study by examining the percentage of women deemed to have uncertain adherence status who are reclassified as adherent, as well as those potential individuals deemed non-adherent in our study who find they are adherent through their women's healthcare providers. This rate of over-referral will be useful when evaluating the impact of the interventions on both subject health and clinical resource utilization.

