## I. PURPOSE OF THE STUDY AND BACKGROUND

Cervical cancer is among the most preventable forms of cancer. Implementation of widespread cervical cancer screening has resulted in a tremendous decrease in the incidence of cervical cancer in the United States and stands as a cornerstone of preventive health efforts. Still, only 80.7% of U.S. women aged 21 – 65 years report adherence to U.S. Preventive Services Task Force (USPSTF) cervical cancer screening recommendations. This rate is far below the *Healthy People 2020* target of 93%. The group identified as most likely to be non-adherent with recommended screening protocols are patients who use the emergency department (ED) for their usual source of care. **The overall goal of the proposed study is to pilot two brief behavioral interventions aimed at improving adherence to cervical cancer screening among ED patients.** The results of this pilot will prepare our interdisciplinary team to successfully compete for NIH funding to scale up the evaluation of the proposed interventions. In order to achieve this goal, we propose to leverage an existing parallel service program in the high volume general population setting of the URMC ED to accomplish the following specific aims:

**Specific Aim 1:** Conduct a randomized pilot trial comparing the efficacies of two structured behavioral interventions in promoting adherence of women aged 21 – 65 to USPSTF cervical cancer screening recommendations: A. Screening & referral and, B. Screening, brief mobile technology-based intervention grounded in the Theory of Planned Behavior (TPB), & referral.

**Hypothesis 1A/1B:** The proposed interventions will improve adherence to USPSTF recommendations at follow-up over baseline levels. Rates of adherence will be greater after Intervention B compared to A.

**Specific Aim 2:** Identify predictors of adherence and non-adherence to USPSTF recommendations at baseline to inform the refinement of the proposed interventions.

[figure not shown]
**Hypothesis 2:** Lower baseline rates of adherence will be identified among ethno-racial minorities, as well as among women with less education, without a usual source of care, and with greater barriers to care.

**Specific Aim 3:** Collect qualitative feedback on perceptions of the interventions to inform their refinement.

[figure not shown]

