**Figure 1. Project Workflow**

After consent, enrollees will complete a ~10-minute computer-adaptive questionnaire, administered at the bedside on a tablet computer by the EDRA to determine adherence to current USPSTF recommendations for cervical cancer screening. The REDCap adaptive screening tool used will be identical to that which was used to gather our preliminary data. The enrollment process will categorize study participants into three groups: adherent, uncertain, or non-adherent (Figure 2). Women found to be adherent will be notified and their participation will conclude (i.e. no follow-up will be performed). Women found to be in the uncertain or non-adherent groups will then be randomized into one of two intervention conditions. Randomization will be automated in the REDCap survey instrument. All women found non-adherent will be referred to their usual care provider. If the patient does not have a usual provider of women's healthcare, she will be referred to UR WHP to receive appropriate screening. [name] (co-I) will maintain an expedited referral pathway to UR WHP for these subjects. [name] or one of the other health care providers at WHP will conduct the screening test. Women for whom adherence is uncertain (e.g. unsure, unable to remember) will be referred to their usual care provider or to UR WHP to confirm their adherence status. If, upon follow-up, the patient was confirmed adherent, she will be retroactively classified as adherent at baseline (though her uncertain status at screening will be retained in the dataset for potential secondary analyses). If confirmed non-adherent, the patient will be retroactively classified as non-adherent at baseline (with initial uncertainty retained). If the patient did not contact a provider to confirm adherence status (and did not remember her status in the 150 day interim), she will remain classified as uncertain.

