### **III. CHARACTERISTICS OF THE RESEARCH POPULATION**

**a. Number of Subjects:** 450

**b. Gender and Age of Subjects:** Women age 21-65. Cervical cancer only occurs in women and cervical cancer screening is only recommended for women aged 21 – 65.

**c. Racial and Ethnic Origin:** We expect the racial and ethnic characteristics of our study population to mirror that of the general patient population of the Emergency Department at Strong Memorial Hospital.

**d. Vulnerable Subjects:** N/A

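### 18% of 450 is 81, not 90: the stated yield, the 0.80 power for Hypothesis 1A and the stated margins of error rest on a count that the planning rate does not give

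*Combined protocol and SAP*

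**What the plan says.** Section XI.a, Plan of Analysis, expects at least 18% "of patients will be non-adherent to screening guidelines" and bases this on earlier research and preliminary data. It continues: "As such, we will enroll 450 patients to identify" at least 90 non-adherent women. Section III.a also gives 450 as the number of subjects.

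The figures that follow in XI.a use that count:

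- **Hypothesis 1A:** with at least 90 "non-adherent subjects across conditions, we will have power of 0.80" for a 10-point improvement over a 15% null, one-tailed, alpha 0.05.
- **Hypothesis 1B:** 45 non-adherent women per condition, power 0.70 for a 24-point difference, one-tailed, alpha 0.10.
- **95% confidence intervals:** margins of at most 10.4% overall and at most 14.8% per intervention.

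Two other figures bear on the rate. For Aim 2, XI.a uses "an expected adherence rate of 0.80". Section I reports that "only 80.7% of U.S. women aged 21 – 65 years report adherence" to the national recommendations. Section II.a sorts women into adherent, uncertain and non-adherent, and says of the uncertain: "If confirmed non-adherent, the patient will be retroactively classified as non-adherent at baseline".

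**The concern.** The plan presents 90 as following from 18% of 450, and it does not. Both figures are stated as lower bounds, so the claim runs from floor to floor: a rate of at least 18% guarantees an expected count of at least 81, not 90. The shortfall carries into the Hypothesis 1A power, the 45 per arm and both margins.

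The plan gives the confidence intervals more weight than the tests, because they are to be used to power the next trial under several scenarios. Limits quoted for that purpose should follow from the plan's own inputs. A reader also cannot tell whether the planning rate is 18% or 20%.

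**Working it through.** **Inputs.** From XI.a: rate at least 18%, 450 women, null 15%, target 25%, one-sided alpha 0.05 for Hypothesis 1A; difference 24 points and one-sided alpha 0.10 for Hypothesis 1B; Aim 2 adherence 0.80. From Section I: national adherence 80.7%. Women lost to follow-up count as failures, so attrition does not shrink the denominator.

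**1. Yield.**
- 0.18 × 450 = 81.
- 90 / 450 = 0.20, and 90 / 0.18 = 500.
- From the national figure: (1 − 0.807) × 450 = 86.9, about 87.

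**2. Power for Hypothesis 1A.** Formula: power = Φ{[0.10 − 1.645 × √(0.15 × 0.85 / n)] / √(0.25 × 0.75 / n)}.
- n = 90: (0.10 − 0.0619) / 0.0456 = 0.834, power 0.798. This reproduces the stated 0.80.
- n = 87: power 0.787.
- n = 81: (0.10 − 0.0653) / 0.0481 = 0.722, power 0.765.
- At n = 81, power of 0.80 needs an improvement of 10.6 points.

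**3. Margins of error.** The plan gives no formula. The stated limits are matched by 1.96 × √[p(1 − p) / (n − 1)] with p = 0.5, the value that makes the margin widest. The usual form divides by n.

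| n | n − 1 form | Usual form | Plan's limit |
|---|---|---|---|
| 90 | 10.39% | 10.33% | 10.4% |
| 45 | 14.77% | 14.61% | 14.8% |
| 81 | 10.96% | 10.89% | 10.4% |
| 41 | 15.50% | 15.31% | 14.8% |
| 40 | 15.69% | 15.50% | 14.8% |

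The stated limits are exceeded only for improvement rates of roughly 35% to 65% (33% to 67% at the widest, by the n − 1 form with 40 women). At the plan's own 25%, the margins are 9.4% to 9.5% overall (n = 81) and 13.3% to 13.6% per arm (n = 41 or 40), inside the limits.

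**4. Power for Hypothesis 1B.** The plan gives no lower rate, so I assume 15% to 40%. With 40 per arm, a 24-point difference, one-sided alpha 0.10 and the pooled-variance normal approximation:
- lower rate 15%: power 0.881
- lower rate 25%: power 0.834
- lower rate 40%: power 0.814

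All three exceed the stated 0.70.

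**5. Chance of finding 90 or more among 450 (binomial).**
- True rate 18%: 0.149.
- True rate 19.3%: 0.372.
- True rate 20%: 0.519.
- An 80% chance needs a true rate of about 21.6%.

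**The case against.** The strongest reply is that the 90 has a source in the same section: the Aim 2 adherence rate of 0.80 leaves 20% of 450, which is exactly 90. On that reading, two planning rates were simply not aligned. This may well be how 90 arose, but it does not repair the text. Section II.a has three groups, and Aim 2 uses a multinomial model, so the 20% who are not adherent would include uncertain women. It is not a rate of non-adherence.

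Other points on that side:

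- **18% is a floor.** The true rate may be higher, and Section I says that people who rely on the ED for care are the least adherent, so the national 19.3% may be low for this setting. That is fair, but no figure in the documents makes 90 a minimum.
- **Uncertain women can be reclassified as non-adherent.** This is so, but no rate is given and XI.a does not invoke it. Section XI.b also foresees women classed as non-adherent who prove to be adherent, which would lower the count.
- **The power statements are conditional on 90 and on 45 per arm, and the 0.80 is right at 90.** This stands. The error lies in the yield, and the later figures inherit it.
- **Method matters as much as the count.** An exact one-sided binomial test gives power of 0.764 at 90 and 0.667 at 81. This also stands. I keep the normal approximation because it reproduces the plan's figure.
- **The per-arm split is not fixed.** Uncertain and non-adherent women are randomised together with no stratification mentioned, so 41 and 40 is a convention, just as 45 and 45 is in the plan.

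**Conclusion.** The concern holds. A yield of at least 90 does not follow from a rate of at least 18% in 450 women; that rate gives 81. On the plan's apparent formulas, the consequences are about 3 points of power for Hypothesis 1A (0.798 to 0.765) and 0.6 to 0.9 points on the margins at their widest. The margin result assumes p = 0.5, which I infer from the match to 10.4% and 14.8%; the plan does not state it. Near the plan's 25% target, the stated margins would still be met. The stated 0.70 for Hypothesis 1B is not shown to be lost. The actual count could reach 90 if the rate is higher or uncertain women are reclassified, but the documents do not support 90 as a minimum. This should be corrected, though it does not threaten the design.

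**What to change.** Choose one planning rate and make XI.a consistent with it.

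1. **Keep 18%.** Restate the expected yield as at least 81 (about 40 per arm). Give Hypothesis 1A power as about 0.76 for a 10-point improvement, or 10.6 points for 0.80 power. Give the margins at p = 0.5 as at most 11.0% overall and at most 15.7% per arm, assuming a near-equal split.
2. **Use 20%, if the preliminary data support it.** State that rate, and present 90 (45 per arm) as the expected count and not a guaranteed minimum; at a true 20%, the chance of reaching 90 is about 52%.

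If women reclassified from uncertain are meant to supply the missing 9, say so and give the assumed rate. In either case, name the formulas used for power and margins.

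The cost is text edits only, with no change to design or conduct. Under option 1 the stated figures become slightly less favourable.

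### Hypothesis 1B is tested without adjustment; one baseline stratum (usual women's health provider, yes/no) would guard the B-versus-A result against chance imbalance at little cost

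*Combined protocol and SAP*

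**What the plan says.** Section XI.a (Plan of Analysis) describes the test of Hypothesis 1B as "a two-sample comparison of post-intervention adherence across intervention conditions", carried out with a chi-square. The power statement begins "Given a one-tailed test with" an alpha of 0.10 and continues: "45 non-adherent subjects in each condition, we will have power of 0.70 to observe a difference as small as 24% in adherence at follow-up". No covariate or stratum is named.

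On allocation, section II.a (text under Figure 1) says that uncertain and non-adherent women are "randomized into one of two intervention conditions" and that "Randomization will be automated in the REDCap survey instrument". It describes no stratification.

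The same section sends a woman to her usual provider or, if she has no usual provider of women's healthcare, says "she will be referred to UR WHP to receive appropriate screening". Her provider status must therefore be known at enrolment. Hypothesis 2 in section I expects lower baseline adherence among several groups, including women "without a usual source of care, and with greater barriers to care".

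Section XI.b repeats the analyses among women referred to UR WHP, that is, those without a usual provider.

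**The concern.** With about 45 women per arm, simple randomisation often leaves a visible difference between arms in any binary characteristic. If that characteristic also predicts whether a woman gets screened, the unadjusted difference between B and A carries part of the imbalance. A pilot yields only one allocation, and section XI.a intends its results to supply effect sizes for powering the next trial. An imbalance favouring B would inflate the B-versus-A effect size taken forward, and one favouring A would shrink it. Provider status is a natural candidate because it is fixed before treatment starts and determines the referral route.

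**Working it through.** **Plan's own figure.** For 45 per arm, one-tailed alpha 0.10 and a 24-point difference, the plan states power 0.70. The reference rate in arm A is not given; the only nearby figure is the Hypothesis 1A comparison "against a null value of 15% improvement". The usual two-proportion formula gives 0.909 (15% vs 39%), 0.867 (25% vs 49%) and 0.847 (38% vs 62%, the minimum), so 0.70 is not reproduced; the stated value is conservative. That is a separate matter, and nothing below depends on it.

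**Inputs.** From the plan: 45 per arm, one-sided alpha 0.10, no strata. Assumed, because the documents give no values: half the women have a provider; screening by 150 days under no treatment effect is 10% without and 30% with a provider (alternatives below); allocation is simple.

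**How often imbalance occurs.** The difference between arms in the number of women with a provider has SD √(2 × 45 × 0.25) = 4.74. More than 10 points means more than 4.5 women, so P(Z > 4.5/4.74 = 0.95) ≈ 0.17 in each direction.

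**Shift in the risk difference.** As a proportion the SD is 4.74/45 = 0.105. Given an imbalance of over 10 points, its mean is about 0.105 × φ(0.95)/0.17 = 0.105 × 0.254/0.17 ≈ 0.157. Multiplied by the 20-point gap in screening, the shift is 0.157 × 0.20 ≈ 0.031, or about 3 points.

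**Conditional error.**
- Overall rate 0.20. The test rejects above 1.282 × √(2 × 0.20 × 0.80/45) = 1.282 × 0.0843 = 0.108.
- Within-stratum variance is (0.10 × 0.90 + 0.30 × 0.70)/2 = 0.15, so the SE given the imbalance is √(2 × 0.15/45) = 0.0816.
- B favoured: (0.108 − 0.031)/0.0816 = 0.94, error about 0.17.
- B disfavoured: (0.108 + 0.031)/0.0816 = 1.70, error about 0.04.

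Simulation, which lets the imbalance vary and respects the discrete counts, gives 0.18 and 0.05.

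**Simulated range** (at least 100,000 trials per case; power at a 16-point effect):

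| Screened, no provider / provider | Chi-square error, all trials | B over 10 points more | B over 10 points fewer | CMH error, either case | Power, chi-square to CMH |
|---|---|---|---|---|---|
| No gap (20% / 20%) | about 0.105 | about 0.10 | about 0.10 | about 0.10 | 0.671 to 0.664 |
| 15% / 25% | about 0.105 | 0.14 | 0.07 to 0.08 | about 0.10 | 0.668 to 0.664 |
| 10% / 30% | about 0.105 | 0.18 | 0.05 | about 0.10 | 0.669 to 0.679 |
| 5% / 35% | about 0.105 | 0.23 | 0.03 | about 0.10 | 0.669 to 0.701 |

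At 15% / 35% power goes from 0.650 to 0.647. When B is favoured, the unadjusted risk difference is off by 3.1 points at 10% / 30% and by 4.7 points at 5% / 35%; the Mantel-Haenszel difference is off by less than 0.1 point.

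**At the plan's 24-point difference.** With 10% / 30%, power goes from 0.893 to 0.897. In a second model with a 25% reference rate and a constant odds ratio, the chi-square has about 0.875, and CMH with two strata has 0.867 (odds ratio 1), 0.882 (3) and 0.898 (5). An extreme odds ratio of 10 gives 0.923.

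**Number of strata.** In the same model, crossing five binary factors (32 strata) lowers power to 0.751 (odds ratio 1) or 0.825 (odds ratio 3).

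**The case against.** A reader might infer that the planned test has the wrong error rate. It does not. Imbalances in the two directions offset each other, and over all randomisations the chi-square error is about 0.105, against 0.101 for CMH. An unadjusted comparison in a randomised pilot is legitimate.

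A reader might also infer that the trial holds known strong predictors of the outcome. The documents do not say so. Hypothesis 2 concerns baseline adherence among all enrollees, gives no strength, and names usual source of care, which is related to a usual women's health provider but is not the same variable. Nothing is said about screening by 150 days among women already found non-adherent or uncertain. The expedited UR WHP pathway (section II.a) and the UR WHP number in the Intervention B texts (Table 1) could narrow any gap. This stands, and it is why the size is shown as a range that includes no effect.

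Nor is adjustment free: a stratum that predicts nothing costs up to about 1 point of power.

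Two further objections stand in part. Section XI.a puts more weight on the overall and arm-specific 95% intervals than on the test, and a stratified test leaves those intervals unchanged. But the B-versus-A effect size is also to inform the next trial, and it can be made less sensitive to imbalance. Section XI.b looks separately at women without a usual provider, but a subset analysis does not adjust the randomised comparison.

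**Conclusion.** The point holds as an optional improvement in robustness and precision; the planned analysis is not in error. If provider status predicts screening by 150 days to the assumed degree (10% versus 30%, half with a provider), about one trial in three (2 × 17% = 34%) has an imbalance of over 10 points. In those trials the one-sided error is 0.18 or 0.05 instead of 0.10, and the risk difference is off by about 3 points. A weaker association (15% versus 25%) gives about 0.14 or 0.07 to 0.08, and no association gives no shift. Stratification holds the error near 0.10 throughout. Average power changes little: up to about 1 point lost if provider status is not prognostic, about 0 to 3 points gained if it is moderately to strongly so. All these sizes rest on assumed prevalence and rates, since the documents supply none.

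**What to change.** In section XI.a, prespecify for Hypothesis 1B a one-sided Cochran-Mantel-Haenszel test at alpha 0.10, stratified only by whether the woman had a usual provider of women's healthcare at enrolment (yes/no). Report the Mantel-Haenszel risk difference with its confidence interval as the B-versus-A effect size, and keep the unadjusted chi-square as a secondary display.

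Two limits belong in the same text. Barriers reported at the 150-day call arise after randomisation and must not be used as strata. Factors should not be crossed into many cells with about 90 women.

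The cost is a sentence or two of wording and a check that provider status is stored as a baseline variable in both arms. Sample size and conduct are unchanged. Prespecification also settles whether to adjust before any imbalance is seen.

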Subjective normative beliefs about screening will be addressed by emphasizing the preponderance of adherence to guidelines in the population. Perceived behavioral control over obtaining cervical screening will be addressed by discussing the accessibility and negligible financial burden of Pap tests. Women who have their own women’s health providers will be instructed to follow-up with these providers or utilize UR WHP, whichever they prefer. To facilitate patient follow through, the message will include hyperlinks to the telephone numbers of the patient’s women’s health care provider (if known) and the WHP.

**c. Follow Up.** All enrollees in the non-adherent and uncertain groups will receive a follow-up call at 150 days (Figure 3). The project coordinator will contact each of these participants by telephone for a brief REDCap questionnaire to determine if they underwent screening, if they learned that they did not require screening, and what barriers they perceived in getting screened or clarifying their adherence. Qualitative feedback regarding perceptions of the interventions will also be solicited from study participants in order to refine the interventions for future study. Relevant domains of feedback will include challenges to adhering with screening guidelines, comfort level with the intervention content discussed in the ED, which TPB message(s), if any, were perceived as most generative of intention to engage in cervical cancer screening, and participant recommendations for intervention revision. Telephone numbers will be confirmed in the ED during enrollment by the EDRA performing the enrollment (e.g., calling patient’s phone to be certain the number is correct), and up to 3 calls will be made to each of these patients to limit unnecessary attrition.

Study team members will use the EPIC medical record to confirm self-reported screening activities among the subjects successfully contacted at follow-up and who report a women’s health provider associated with UR Medicine. No confirmation will be sought among subjects reporting cervical screening with providers outside of the UR Medicine system.

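### The 0.80 power for Hypothesis 1A allows for no loss to follow-up, although lost women are scored as failures; at a true rate of 25% it falls to 0.62 with 10% loss and 0.39 with 20%

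*Combined protocol and SAP*

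**What the plan says.** All the design figures are in section XI.a (Plan of Analysis) of the combined protocol and SAP.

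- **Test of Hypothesis 1A.** "The first test will compare % adherent at follow-up against a null value of 15% improvement". The null is described as the share of non-adherent women who would become adherent over 150 days with no intervention. The plan adds that it regards this value as unrealistically high and chose it so as not to overstate the interventions.
- **Power.** With a one-tailed alpha of 0.05 and at least 90 non-adherent women pooled over both conditions, "we will have power of 0.80 to observe improvement as small as 10% over the null".
- **Intervals.** The plan ranks these above the tests. It gives 95% margins of at most 10.4 points overall and 14.8 points per intervention, and will use the intervals to power the next trial under expected, ideal and worst-case scenarios.
- **Loss.** "Patients lost to follow-up will be considered intervention failures (i.e. non-adherent) in accordance with intention-to-treat principles".

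Section II.c (Follow Up) sets one telephone contact at 150 days and says that "up to 3 calls will be made to each of these patients to limit unnecessary attrition". It limits the check of self-reported screening against the medical record to women who were successfully contacted and who have a UR Medicine provider. No expected contact or loss rate appears anywhere.

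**The concern.** The power statement and the rule for lost women do not fit together. Lost women stay in the denominator and cannot count as successes, so the expected observed rate is the true rate multiplied by the contact rate. The null receives no matching reduction, because it is defined for all non-adherent women, reached or not. Every percentage point of loss therefore narrows the 10-point gap on which the study is sized.

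Two things are at stake. First, a reader will take 0.80 as the chance of confirming Hypothesis 1A if the interventions bring 25% of women up to date, and that chance may be much lower. Second, the intervals are the pilot's main product. If they are computed only with losses as failures, the expected scenario for the next trial is built on a rate that mixes uptake of screening with success in reaching women by telephone.

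**Working it through.** **Inputs from section XI.a:** null p0 = 0.15; alternative 0.25 (15% plus 10 points); one-sided alpha 0.05 (z = 1.645); n = 90 overall and 45 per condition, taken as stated.

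**Assumptions:** the contact rate c is not given, so a range is shown. Contact is taken to be unrelated to screening.

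**Step 1: reproduce the plan's 0.80.** One-sample normal approximation:

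power = Φ{[(p1 − p0)√n − 1.645√(p0(1 − p0))] / √(p1(1 − p1))}

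With p1 = 0.25: (0.10 × 9.487 − 1.645 × 0.357) / 0.433 = (0.949 − 0.587) / 0.433 = 0.835, and Φ(0.835) = 0.798. This matches 0.80 with no loss. The exact binomial test rejects at 20 or more of 90 (actual alpha 0.043; a cut-off of 19 would give 0.074), and its no-loss power is 0.764.

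**Step 2: score losses as failures.** Keep n = 90 and replace p1 by 0.25 × c. For c = 0.90, p1 = 0.225: (0.712 − 0.587) / 0.418 = 0.297, and Φ(0.297) = 0.617.

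| Contact | Expected observed rate | Power, normal approximation | Power, exact test |
|---|---|---|---|
| 100% | 25.0% | 0.80 | 0.76 |
| 95% | 23.75% | 0.72 | 0.67 |
| 90% | 22.5% | 0.62 | 0.57 |
| 85% | 21.25% | 0.51 | 0.45 |
| 80% | 20.0% | 0.39 | 0.34 |
| 70% | 17.5% | 0.18 | 0.15 |

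The normal column is the one to compare with the stated 0.80. The exact column should be compared with 0.76.

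**Step 3: the other reading of 25%.** Suppose 25% is the rate after losses are scored. On the normal formula, 0.80 power needs an observed rate of 25.03%, so the true rate must be 25.03% / c: 27.8% at 90% contact, 31.3% at 80% and 35.8% at 70%.

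**Step 4: interval margins.** The maximum margin is 1.96√(0.25/n) = 10.3 points at n = 90 and 14.6 at n = 45. With n − 1 in the denominator the values are 10.4 and 14.8, as stated. Loss changes neither n, so both bounds hold. At an observed 22.5% or 20% the overall Wald margin is narrower, at 8.6 or 8.3 points.

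**Step 5: interval centring.** The interval is centred near 0.25 × c, which is 2.5 points low at 90% contact and 5 points low at 80%. Coverage of a true 25% by a nominal 95% Wilson interval at n = 90, summing the binomial probabilities at rate 0.25 × c, is:

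| Contact | Coverage of the true 25% |
|---|---|
| 100% | 0.95 |
| 90% | 0.92 |
| 80% | 0.82 |
| 70% | 0.63 |

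**The case against.** The strongest reply is that the tested endpoint is adherence at follow-up, and the plan defines lost women as non-adherent on it. On that reading 25% already includes the failures and 0.80 is correct as written. This stands as a possible reading. But the plan does not say so, and it would mean that the study is sized for a true rate above 25%.

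A second reply is that the plan is deliberately conservative: the null was set high on purpose, and counting losses as failures is a familiar cautious choice. That supports keeping the rule. It does not support quoting power as if the rule cost nothing. It does weaken any inference that a useful intervention would necessarily be missed.

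A third is that medical records could supply outcomes for unreached women. The follow-up confirmation in section II.c covers only contacted women. The separate five-year record review covers all enrolled women, but its stated purposes are to validate self-report and to gauge awareness of screening schedules. Neither is described as changing the outcome of a woman who is lost.

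Three stronger conclusions are tempting and are not supported:

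- *The stated margins fail.* They do not; they are bounds at fixed n and survive any loss (step 4).
- *Power drops from 0.80 to 0.57 at 10% loss and 0.34 at 20%.* That sets a normal-approximation figure against exact-test figures, so part of the drop is a change of method.
- *Hypothesis 1A would usually fail and the intervals would often miss the true rate.* At 10% loss, power is still above one half and coverage is 0.92. Since no loss rate is given, these consequences can only be stated conditionally.

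**Conclusion.** The point holds in a limited form. The arithmetic behind 0.80 is sound, but the figure assumes complete follow-up, while the same paragraph makes incomplete follow-up count against the interventions. If 25% is the true rate among all women, the stated power is not delivered: 5% loss already takes it to 0.72, about 15% loss takes it to roughly one half, and 20% loss roughly halves it. If 25% is the rate after losses are scored, the power stands and the unstated requirement is a higher true rate. Either way the reader needs a contact rate and a definition, and the plan gives neither.

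For the intervals, the fault is downward bias in the estimated improvement rate, not width. It is modest at 10% loss and substantial at 20% to 30%.

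These sizes rest on assumed contact rates and on contact being unrelated to screening. If screened women are easier to reach, fewer successes are lost and the fall in power is smaller; if they are harder to reach, it is larger.

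**What to change.** In section XI.a:

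1. State whether the 25% is before or after lost women are scored as failures.
2. State an assumed contact rate and restate the power at that rate, using one method throughout. Possible wording on the plan's normal approximation: *with unreached women scored as failures, 0.80 power requires a true rate of about 28%, 31% or 36% at 90%, 80% or 70% contact.*
3. Keep losses as failures for the primary analysis, and label the resulting intervals as the conservative, worst-case basis.
4. Add overall and condition-specific intervals among contacted women as a second basis for powering the next trial. Note that they are unbiased only if contact is unrelated to screening, and may be too high if screened women are easier to reach.

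The cost is some protocol wording, one more set of intervals and a less favourable power statement. No extra patients are needed.
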